6.1. Study Design

Patients receiving aRCC treatment (see [Table 4](#)), between April 2018 and the present, who have no prior aRCC treatment in their claims history will be identified for this study. The index date for each analysis will be defined as the date of initiation of the aRCC treatment. Patients must have at least 2 RCC diagnoses at least 30 days apart to be included. Patients must also have 2 secondary malignancy ICD9 or ICD10 codes (often used in claims data to suggest cancer metastases) at least 30 days apart in the 12 months pre and one month post index aRCC treatment. [CCI](#)

Various algorithms and temporal relationships between the secondary malignancy codes, RCC diagnosis codes and other cancer codes were explored toward developing the criteria for metastatic advanced RCC for this study.

Study will require a minimum of 12 months of enrollment prior to the index date. Feasibility was assessed for various lengths of continuous enrollment criteria (3, 6 and 12 months post index date) toward understanding sample sizes available for analysis and follow-up periods. Study outcomes will be assessed for three patient cohorts (3, 6 and 12 month cohorts) according to their available months of continuous enrollment.

PFIZER CONFIDENTIAL

First line therapy cohorts will first be presented for all patients regardless of follow-up time available. Baseline characteristics, costs and utilization will be measured over the 6 months prior to the index date. Duration of therapy and utilization analysis will require at least 6 months of post-index enrollment, with sub-analysis preformed on the cohorts with 3-months and 12-months of post-index enrollment. Utilization and cost will be performed per-utilizer-per-month (PUPM), and then separately for each of the cohorts with 3-month, 6-month and 12-months of post-index enrollment.

The analysis will focus on, but is not limited to, the following regimens:

- a. **Combo IO:** nivolumab combined with ipilimumab;
- b. **Monotherapy TKI:** sunitinib, cabozantinib, and pazopanib;
- c. **Combo TKI + IO:** avelumab in combination with axitinib, pembrolizumab in combination with axitinib;
- d. **Other:** all others regimens.

PFIZER CONFIDENTIAL

[figure not shown]
[figure not shown]
[figure not shown]

Figure 1: Cohort Identification

Analysis 1. Treatment Patterns and Duration

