6.2.1. Inclusion Criteria

Subjects will be selected irrespective of their survival status. Patients must meet all of the following inclusion criteria to be eligible for inclusion in the study:

- **Index date:** The first prescription or administration of one of the medications indicated for advanced RCC recorded in the database between April 2018-March 31, 2019, among those with no aRCC treatment in their history.
- Age 18 years or older in the year of the index first line therapy prescription.
- 2 or more RCC diagnoses (ICD-9: 189.0; ICD-10: C64.1, C64.2, C64.9) at least 30 days apart, in the 1 year prior to the index date until 30 days post index date.

PFIZER CONFIDENTIAL

- 2 or more code for secondary malignancy codes indicating possible diagnoses for metastatic disease at least 30 days apart, in the 1 year prior to the index date until 30 days post index date. (ICD-9: xx-199.xx; ICD-10: C77-C79, except ICD9: 198.0 Secondary malignant neoplasm of the kidney and ICD10: C79.0 Secondary malignant neoplasm of the kidney and renal pelvis).
 - CCI [REDACTED]
- Continuous enrollment from 12 months prior to the index date. Patients will be required to have continuous enrollment from their index date until the end of the available data. This will allow for sub-analysis of cohorts with 3 months, 6 months and 12 months of available data.

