6.2.2. Exclusion Criteria

Patients meeting any of the following criteria will not be included in the study:

- Received advanced treatment prior to the study index date.
- Prescription records with negative days of supply will be excluded from all the analyses except in cost variable calculation. The day of supply for claims with missing or 0 days will be imputed.
- Only one RCC diagnosis in the 12 months prior or one month post index date.
- Patients with data for analysis (<3 months post index date).

PFIZER CONFIDENTIAL

[REDACTED]

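### The post-index enrolment rules state no exemption for death, contradict selection regardless of survival, and make survival 100% up to each cohort's own minimum

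*Combined protocol and SAP*

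**What the plan says.** Section 6.2.1 (Inclusion Criteria) contains two statements that pull apart: "Subjects will be selected irrespective of their survival status" and "Patients will be required to have continuous enrollment from their index date until the end of the available data". The second is followed by "This will allow for sub-analysis of cohorts with 3 months, 6 months and 12 months of available data".

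Section 6.2.2 (Exclusion Criteria) lists "Patients with data for analysis (<3 months post index date". A word seems to be missing; the likely sense is a 3-month minimum.

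Section 6.1 (Study Design) says "Study outcomes will be assessed for three patient cohorts (3, 6 and 12 month cohorts) according to their available months of continuous enrollment" and "Duration of therapy and utilization analysis will require at least 6 months of post-index enrollment". On costs it says "Utilization and cost will be performed per-utilizer-per-month (PUPM), and then separately for each of the cohorts". The same section promises to show the first-line groups in every patient first, whatever their follow-up.

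Elsewhere the plan expects deaths. Death ends treated time and the outcomes period (6.1, Analyses 1 and 3), ends a line of therapy and is an end-of-follow-up status (Table 5), and is a time-to-treatment-failure (TTF) endpoint (Section 5, Table 7). Landmark survival is planned at 3, 6 and 12 months (6.1, Table 7), the same times as the enrolment minimums. Section 6.7 plans Kaplan-Meier curves for duration of therapy and survival.

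**The concern.** A minimum period of post-index enrolment is information from after time zero. If enrolment stops at death, the minimum works as a survival requirement, and patients who die early leave the analysis. The rules that mention death do not repair this: they end observation for patients already included and do not admit those who died before the minimum.

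At stake are the Objective 3 outcomes: TTF and duration, utilization, the cohort versions of cost, and possibly landmark survival. The study is meant to show unmet need, and losing early deaths makes outcomes look better than they are. The text can also be programmed in several ways. Because the databases may not be merged and results are to be replicated across them, different readings could pass for differences between data sources.

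**Working it through.** The plan states no sample size, expected survival or disenrolment rate, so there is no planned figure to reproduce.

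**Step 1: the structural result (no rates needed).** Assume death ends enrolment, which the documents do not state. With S the true survival from index and entry conditional on m months of enrolment, apparent survival at t is 1 for t ≤ m and S(t)/S(m) for t > m. The ratio form also assumes that disenrolment is unrelated to death. A ≥3-month cohort therefore shows 100% at 3 months, a ≥6-month cohort 100% at 3 and 6, and a ≥12-month cohort 100% at all three landmarks.

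**Step 2: where it applies.**
- *Duration and utilization:* the 6-month minimum is explicit in Section 6.1.
- *3-month survival:* applies if the Section 6.2.2 exclusion is read as a minimum.
- *6- and 12-month survival:* applies if the enrolment cohorts that Section 6.1 sets up for study outcomes are used for survival. No section names the survival denominator.
- *Costs:* early deaths are lost from the per-cohort versions; they are lost from the per-month version only through Sections 6.2.1 and 6.2.2.

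**Step 3: what the end of available data means.** If it is the database cut-off, nobody who died beforehand qualifies: survival reads 100% and every regimen difference is zero. If it is each patient's own last data, that sentence removes no deaths, but the 3-, 6- and 12-month minimums still do.

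**Step 4: illustrative size under the second meaning.** Assumptions: constant hazard, true 12-month survival S12 of 65% to 85%, S(m) = S12^(m/12).

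| Quantity | S12 = 65% | S12 = 85% |
|---|---|---|
| S(3) | 0.65^0.25 = 0.898 | 0.85^0.25 = 0.960 |
| S(6) | 0.65^0.5 = 0.806 | 0.85^0.5 = 0.922 |
| Deaths before month 3 / month 6 | 10.2% / 19.4% | 4.0% / 7.8% |
| 12-month survival, ≥3-month cohort | 0.65/0.898 = 72.4% | 0.85/0.960 = 88.5% |
| 12-month survival, ≥6-month cohort | 0.65/0.806 = 80.6% | 0.85/0.922 = 92.2% |

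**Step 5: TTF.** If non-fatal failure is independent of death and disenrolment is censored, the true 6-month failure-free share is S(6) times the share free of non-fatal failure. The ≥6-month set estimates only the latter, so the overstatement factor is 1/S(6): 1/0.922 = 1.08 to 1/0.806 = 1.24.

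**Step 6: regimen differences.** Under constant hazard, a true gap of 85 − 65 = 20 points reads 88.5 − 72.4 = 16.1 (≥3 months) or 92.2 − 80.6 = 11.6 (≥6 months). With other hazard shapes it can widen. If both regimens have S(6) = 0.90, the ≥6-month cohort reads 0.85/0.90 = 94.4% and 0.65/0.90 = 72.2%, a gap of 22.2.

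**Step 7: exempting only deaths.** Let L = −ln S12, M = −ln(1 − d) for annual disenrolment d (assumed 10–30%), and e = exp(−(L + M)). Crude 12-month survival is then e / [e + (L/(L+M))(1 − e)]. For S12 = 65% this gives 63.7% (d = 10%) and 60.4% (d = 30%); for 85%, 84.3% and 82.4%. The shortfall is 0.7 to 4.6 points, because living patients who leave the plan are still dropped.

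**Step 8: simulation.** One million simulated patients per setting reproduced Steps 4 and 7 to within 0.1 point. Kaplan-Meier in all indexed patients, censored at disenrolment, returned 65.0% and 85.0–85.1%.

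**The case against.** - *The survival-status sentence is itself the exemption.* That may be the intent, and with deaths expected elsewhere it makes the database cut-off the least plausible meaning. But nothing carries the exemption into Sections 6.1 or 6.2.2, and a death-only exemption still leaves survival low (Step 7).
- *Survival may be analysed in all patients.* Section 6.1 does promise a first presentation without a follow-up minimum. It does not say that survival is estimated there, and it conflicts with Section 6.2.2 read as a minimum. The 6-month rule for duration and utilization stands either way.
- *Short data explain the cohorts.* The protocol is dated 4 October 2019 and Section 6.2.1 indexes patients to 31 March 2019, so about 6 months were then available for the latest patients. That is a fair reason for 3-, 6- and 12-month cohorts, but potential follow-up to the cut-off meets it without selecting on survival.
- *Some text cannot be seen.* Figure 1 (Cohort Identification) is not shown and might carry an exemption. Monthly MarketScan enrolment records (Section 6.4) could also admit a death in the final month of a minimum.
- *The study is descriptive and survival exploratory.* True, and no test or sample size depends on it. TTF, costs and utilization are nevertheless listed objectives.

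A reader might infer three stronger things. One is that the plan certainly removes every death; this holds only under the cut-off meaning. Another is that regimen differences must shrink; Step 6 shows that the direction depends on the hazards. The third is a larger TTF factor, up to 1/(0.806 × 0.837) = 1.48 if leaving the plan counts as failure, with √0.70 = 0.837 still enrolled at 6 months. Section 5 and Table 7 do list end of enrolment within TTF, but that mixes a censoring event with failure, so the excess over 1.24 is not survivor selection.

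**Conclusion.** The point holds and should be corrected before cohorts are built. The enrolment rules conflict with the survival-status sentence, with the deaths expected elsewhere, and with the all-patient presentation in Section 6.1. Given that death ends enrolment, 100% survival to a cohort's own minimum follows by construction. This is firm for the 6-month duration and utilization set and conditional for survival, as Step 2 sets out.

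Survival is overstated wherever a minimum is applied without a death exemption. In the Step 4 illustration, 12-month survival is too high by 3.5 to 7.4 points (≥3 months) or 7.2 to 15.6 points (≥6 months), and the 6-month failure-free share by a factor of about 1.08–1.24. These sizes rest on assumed rates. What the documents themselves establish is the contradictory population definition.

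**What to change.** Reconcile Sections 6.1, 6.2.1 and 6.2.2:

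1. Set enrolment eligibility at or before index. Keep the 12-month pre-index rule; remove the post-index enrolment criterion and the 3-month exclusion.
2. Define the 3-, 6- and 12-month cohorts by potential follow-up: index date at least that long before the database's stated cut-off. Keep patients who die or disenrol.
3. Estimate landmark survival and TTF/duration from index in all eligible patients with the Kaplan-Meier method of Section 6.7, censoring at disenrolment or data end. Report survival only where death data exist.
4. Amend the TTF definition (Section 5, Section 6.1, Tables 5 and 7) so that end of enrolment is censored and not counted as failure.
5. Use observed person-months as the denominator for per-month costs and utilization.

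Exempting deaths alone would remove most of the bias, but it is second best (Step 7).

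Secondary: the diagnosis codes may be collected "in the 1 year prior to the index date until 30 days post index date", and the combination-therapy rule in Table 5 (partly redacted) looks 30 days ahead. Both can be noted as limitations.

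Cost: protocol wording and a re-run cohort query, with no new data. Some patients contribute shorter follow-up, per-month estimates become more variable, and databases without death data still cannot separate death from disenrolment.

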Regimen change (switching)	Categorical: Yes/No At least one non-index advanced/metastatic RCC medication during or after the period of the last persistent index medication prescription's days supply plus the 30 day gap (and before re-initiation of index medication or follow-up, if after).
Regimen change (augmentation)	Categorical: Yes/No Addition of treatment to initial therapy prescribed, ie, initiation of a new therapy different from the initial therapy while continuation of the initial therapy.
Line of therapy definitions	Categorical: 1L vs. 2L vs. >=3L.
Treatment sequence	Categorical: Based on observed treatment sequences. Treatment Sequence – Sequence of successive therapies for mRCC from 1L to 2L to 3L (stop after 3L).
Patient's status at end of follow-up	Categorical: end of enrollment, end of data availability, death. Patient is in one of the following mutually exclusive categories at the end of follow-up.

PFIZER CONFIDENTIAL

[figure not shown]

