6.6. Data Management

All databases used in this study comply with both the spirit and the letter of the Health Insurance Portability and Accountability Act of 1996 (HIPAA). These databases meet the criteria for a limited-use dataset and contain none of the data elements prohibited by HIPAA for limited-use datasets. Tables will be regenerated on a periodic basis based on scheduling of database updates and refreshes. This study will use a combination of analytical tools, Boston Health Economic's Instant Health Data (IHD) tool, with ad hoc programming performed using SAS software, version 9.4 (SAS Institute Inc, Cary, NC) or R software for statistical computing and graphics supported by the R Foundation for Statistical Computing.

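### Requiring enrollment through the end of the database excludes living patients who already have the months each cohort needs, and contradicts the rest of the protocol

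*Combined protocol and SAP*

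**What the plan says.** Section 6.2.1 introduces its list with "Patients must meet all of the following inclusion criteria to be eligible for inclusion in the study". One item, after the 12-month look-back, is: "Patients will be required to have continuous enrollment from their index date until the end of the available data". The reason given is: "This will allow for sub-analysis of cohorts with 3 months, 6 months and 12 months of available data". No length, cap or exception is attached. The same section says "Subjects will be selected irrespective of their survival status" and sets the index date as a first treatment "recorded in the database between April 2018-March 31, 2019".

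Other sections describe a different rule:

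- Section 6.1 assigns patients to the 3-, 6- and 12-month cohorts "according to their available months of continuous enrollment". It first presents the first-line cohorts for everyone, whatever their follow-up.
- Section 6.1 (outcomes study period and TTF), Table 5 in 6.3.1 (discontinuation date) and Table 7 in 6.3.3 (TTF) all list end of enrollment as one of the ways observation ends.
- Table 5 defines status at end of follow-up as "Categorical: end of enrollment, end of data availability, death", so disenrollment and end of data are separate outcomes.
- Section 6.6 adds: "Tables will be regenerated on a periodic basis based on scheduling of database updates and refreshes".

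**The concern.** The cohorts need 3, 6 or 12 months of enrollment. The criterion asks for something else: enrollment to the last date in the database. A patient with 14 complete months who then changes insurer fails it and drops out of every cohort, including the 12-month one. For living patients, the end-of-enrollment status in Table 5 could never be used.

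The length demanded also varies. It equals data end minus index date, so early starters face a longer requirement than late ones. When the tables are re-run on refreshed data it lengthens again, and a patient counted in one version can vanish from the next.

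At stake are usable sample, reproducibility across refreshes and across four databases that may not be merged, and the survival estimates if decedents stay in while living leavers are removed. Section 6.7 says there is no separate SAP, so this wording is what will be programmed.

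**Working it through.** The plan states no sample size, disenrollment rate or data cut-off, so there is no figure of its own to reproduce.

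**1. Required length.** Input: the index window in 6.2.1, taken as 1 April 2018 to 31 March 2019. Length = data end − index date, for assumed data ends:

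| Assumed data end | First starter | Last starter |
|---|---|---|
| 30 Jun 2019 | 14.9 months | 3.0 months |
| 30 Sep 2019 | 18.0 | 6.0 |
| 31 Dec 2019 | 21.0 | 9.0 |
| 31 Mar 2020 | 24.0 | 12.0 |

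The gap is about 12 months at every cut. Each quarterly refresh adds about 3 months for everyone already included.

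**2. Living patients excluded.** Assumptions: constant monthly exit h of 1%, 2% or 3%; index dates uniform over the window; data ending 18 months after it opens; deaths ignored. The share excluded at required length k is 1 − (1 − h)^k.

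| | h = 1% | h = 2% | h = 3% |
|---|---|---|---|
| Last starters, k = 6 | 5.9% | 11.4% | 16.7% |
| First starters, k = 18 | 16.5% | 30.5% | 42.2% |
| Average, k uniform on 6 to 18 | 11.3% | 21.3% | 30.2% |
| Fixed 6-month rule, any index date | 5.9% | 11.4% | 16.7% |
| Excess of average over fixed rule (points) | 5.4 | 9.9 | 13.5 |

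Among patients who already have 6 months, the further exclusion is the average of 1 − (1 − h)^j for j uniform on 0 to 12, that is 1 − [1 − (1 − h)^12] / [−12 ln(1 − h)]:

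- h = 1%: 1 − 0.1136/0.1206 = 5.8%
- h = 3%: 1 − 0.3062/0.3655 = 16.2%

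**3. Effect on survival if deaths are kept and living leavers dropped.** Assumptions: exponential death hazard m and exit hazard c, required length T. With a = m + c:

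- Retained = (m/a)(1 − e^(−aT)) + e^(−aT)
- Deaths by month 12 = (m/a)(1 − e^(−12a))
- Apparent 12-month survival = 1 − deaths/retained

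Take true survival of 70% (m = 0.02972 per month), 20% annual exit (c = 0.01860) and T = 21. Deaths are 0.6152 × 0.4400 = 0.2707. Retained is 0.6152 × 0.6375 + 0.3625 = 0.7547. Apparent survival is 1 − 0.2707/0.7547 = 64.1%. At 10% and 30% annual exit it is 67.3% and 60.4%.

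With T = 12, the fixed 12-month-or-death rule, the same formula gives 68.8%, 67.4% and 65.8% at 10%, 20% and 30% exit. The bias is smaller but still present, because living leavers before month 12 are still dropped. Only censoring at disenrollment removes it in this model.

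**The case against.** The best defence is that the sentence is loosely worded. The one after it uses available data to mean the months a patient has. Read that way, the criterion asks only for unbroken enrollment through each patient's own record, which agrees with 6.1 and Table 5. The exclusion in 6.2.2 of patients with under 3 months points the same way: if data end at 18 months, the literal rule already guarantees every living patient at least 6 months. This is good evidence that censoring may have been intended. It does not rescue the text, because on that reading the criterion sets no length of enrollment at all. Eligibility is also applied before any follow-up variable is computed.

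Other objections stand and limit the point:

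- The 11-30% is a gross loss. It nearly equals what a fixed 12-month rule would exclude (11.4% to 30.6%), so a reader should not take it as the net effect.
- A reader might infer biased regimen comparisons, because nivolumab plus ipilimumab was approved as the window opened. The documents give no uptake by calendar time, and the calculation uses one exit rate for all.
- A reader might infer systematic loss of patients turning 65. Section 6.2 and Table 6 include Medicare, and section 6.4 describes Medicare Supplemental files and over 10 million PharMetrics enrollees above 65.
- A reader might infer that each refresh shrinks the study. Section 6.1 runs the index window to the present, so a refresh may also add patients.
- That deaths are exempt is inferred from "Subjects will be selected irrespective of their survival status"; no exception is written. The objectives confine survival analysis to Optum Clininformatics, and section 6.1 adds PanTher. Where death is not recorded, it may appear as disenrollment and remove decedents too.
- The 24-month post-index analysis window in the Optum text of 6.4 might act as a cap, but it is not written as one. It would matter only for data ending after about March 2020.

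The study is descriptive and disclaims causal inference. That lowers the stakes but leaves the question of who enters the cohort.

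**Conclusion.** Wrong as written. Followed literally, the criterion removes living patients who already have the months their cohort needs, contradicts sections 6.1, 6.3.1 and 6.3.3, and sets a requirement about 12 months longer for the first starters than for the last. These conclusions follow from the text and the dates alone.

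The size rests on assumptions. With 1-3% monthly exit and data ending 18 months after the window opens, the excess over a fixed 6-month rule is about 5-14 points, or 5.8-16.2% of patients who already have 6 months. If deaths are retained, the direction of the survival bias is downward; its amount depends on assumed exit and death rates. Differential bias between regimens is not established.

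**What to change.** Replace the post-index sentence in 6.2.1 with:

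> The 3-, 6- and 12-month cohorts require continuous enrollment for 3, 6 or 12 months after index, or until death if earlier. No patient is required to remain enrolled to the end of available data. Follow-up ends (is censored in time-to-event analyses) at disenrollment or the data cut-off, or ends at death.

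The death clause is essential. Without it, anyone dying before month 3, 6 or 12 leaves that cohort, and landmark survival in the matching cohort becomes 100% by construction.

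Four further edits are needed:

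- State one dated data cut-off per database, and report each refresh against its own date.
- Reconcile the under-3-months exclusion in 6.2.2 with the all-patient presentation in 6.1.
- Take landmark survival from the Kaplan-Meier curves already planned in 6.7, over all eligible patients with censoring at disenrollment, and make the TTF definitions say the same about end of enrollment.
- Note among the limitations in 6.9 that, where death is not recorded, it may appear as disenrollment.

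The cost is a few sentences. No new data are needed, and dropping the end-of-data requirement can only add usable patients.
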